The study includes a screening period of up to 35 days (with 2 screening visits) and a treatment period of approximately 12 months (52 ± 2 weeks) (with 6 treatment/observational visits) plus an additional follow-up at a pulmonary laboratory 4 to 5 weeks after the last treatment/observational visit. A longer screening period may be permitted with approval from the Sponsor. Planned treatment/observational visits will occur at 0 (pre-dose, baseline) and approximately 1, 3, 6, 9, and 12 months. For the CVT-301 treatment group, these visits will be treatment visits and for the observational cohort, these will be observational visits. All patients, regardless of treatment group, will be required to attend all of the screening visits and all of the treatment/observational visits. Assessments for DLco will be performed at a pulmonary laboratory outside of the clinic prior to the TV/OV1, within 2 weeks prior to the 3-, 6-, 9-, and 12-month visits, and 4 to 5 weeks after TV/OV6.

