12.1. Determination of Sample Size

Approximately 250 CVT-301 treatment patients and 115 control patients will be enrolled in this study. It is assumed that the drop-out rate will be approximately 25%.

Assuming that there is no difference in the changes from baseline between the CVT-301-treated patients and the observational cohort in regards to FEV1, the study has the following power for the comparison between the 2 groups. The upper limit of the 95% confidence interval for the difference between the 2 groups in change from baseline in FEV1 will be less than 0.121 L with 90% power, assuming 188 and 86 patients completing the study in the CVT-301 treatment group and observational cohort, respectively.

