12.5. Safety Analysis

The disposition of the patients will be summarized by tabulating the number of screened, randomized, completed, and discontinued patients. The reasons for premature discontinuations will be tabulated.

The extent of exposure to study treatment will be summarized for the patients who received CVT-301 treatment. The time period between TV/OV1 and TV/OV6 (or Early Withdrawal Visit) will be used as the measure of extent of exposure for the patients randomized to the observational cohort. Adverse events will be tabulated by treatment group according to the Medical Dictionary for Regulatory Activities (MedDRA). Study-emergent and treatment-emergent adverse events (TEAEs) will be summarized by body system and preferred term. For patients in the observational cohort, the AEs collected between TV/OV1 and TV/OV6 (or Early Withdrawal Visit) will be considered as TEAEs. Furthermore, the time of onset of the TEAEs will be summarized.

For vital signs, ECG parameters, spirometry measurements, and DLco, the changes from pre-dose to post-dose assessments of the corresponding day will be calculated and described using descriptive statistics. For spirometry, DLco, and safety laboratory variables, the differences in pre-dose values between the study days will be described. Furthermore, the changes in the spirometry values and difference between the groups will be estimated using a Mixed Model for Repeated Measurements (MMRM) similar to the one used for the efficacy variables. The proportion of patients with abnormal spirometry values will be tabulated using different criteria for the threshold (e.g., at least 10% or 20% change from baseline at any single visit, at least 10% or 20% change from baseline on at least 2 consecutive visits). The proportions of patients meeting ATS quality criteria (and also for those 'rejected') will be summarized. All spirometry analyses will be performed both for all patients regardless of the ATS quality criteria and separately excluding the assessments not meeting the ATS quality criteria.

At least the following variables will be analyzed:

- Vital signs: standard and orthostatic systolic and diastolic BP and HR.
- ECG: HR, PR, QRS, QT and RR intervals, QTcB (Bazett's correction formula calculated as $QT/RR^{1/2}$) and QTcF (Fridericia's correction formula calculated as

QT/RR^{1/3}). ECG parameter values or parameter changes of potential clinical concern will be tabulated.

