12.6. Exploratory Efficacy Analysis

The derivation of the exploratory efficacy variables will be defined in detail in the SAP.

The changes from baseline in continuous exploratory efficacy variables will be estimated using an MMRM. The model will include visit and the stratification variables (Hoehn and Yahr stage and screening FEV1 and/or FEV1/FVC) as fixed factors. The baseline value will be used as a covariate. For variables which do not have a pre-treatment baseline assessment, OFF-state baseline UPDRS Part 3 score will be used as the baseline covariate. An unstructured covariance structure will be applied for the MMRM. In case the model will not converge with the unstructured covariance structure, compound symmetry will be used instead.

The sensitivity analyses will be specified in the SAP. Sensitivity analysis will be performed at least for the method to handle missing data (e.g., last observation carried forward, pattern mixture model using multiple imputation instead of MMRM), definition of analysis population (e.g., patients completing the study instead of observed cases), and statistical method (e.g., analysis of covariance [ANCOVA] models separately for each visit instead of MMRM).

The categorical data will be primarily evaluated descriptively. Each visit will be evaluated separately for the categorical endpoints.

The exploratory efficacy data collected from the patients in the observational cohort will be summarized with descriptive statistics.

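### Compound symmetry is the only fallback if the unstructured MMRM does not converge; if used, it misstates the month-12 interval whenever variability changes over follow-up (minor)

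*Protocol*

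**What the plan says.** Section 12.6 (Exploratory Efficacy Analysis) sets the starting point: "An unstructured covariance structure will be applied for the MMRM". It then gives the single replacement: "In case the model will not converge with the unstructured covariance structure, compound symmetry will be used instead". It names no intermediate structure and no robust variance estimator. The model described there has visit and the stratification variables as fixed factors and baseline as a covariate.

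Section 12.5 (Safety Analysis) has the spirometry changes and the difference between groups estimated "using a Mixed Model for Repeated Measurements (MMRM) similar to the one used for the efficacy variables". It states no covariance structure or fallback of its own.

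Section 7 fixes the visits: "Planned treatment/observational visits will occur at 0 (pre-dose, baseline) and approximately 1, 3, 6, 9, and 12 months". That makes five post-baseline visits. Section 12.1 gives the numbers: "Approximately 250 CVT-301 treatment patients and 115 control patients will be enrolled in this study", and a precision statement for the FEV1 difference (upper 95% limit below 0.121 L with 90% power) "assuming 188 and 86 patients completing the study in the CVT-301 treatment group and observational cohort, respectively".

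**The concern.** The rule goes from a structure in which every visit has its own variance straight to one in which all visits share a variance and all pairs of visits share a correlation. Structures between these two, which keep a separate variance per visit but simplify the correlations, are passed over.

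For a 12-month safety study the last visit matters most. If changes from baseline are more variable at month 12 than earlier, a common variance borrows the smaller early values and the printed month-12 standard error is too small. If they are less variable at month 12, the error goes the other way. FEV1, FVC and their ratio carry the primary objective, and estimating the group difference on pulmonary measures is a secondary objective (Section 6). If the spirometry model does follow the rule, the figure affected is the interval for that difference.

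**Working it through.** **Inputs from the protocol.** 250 and 115 patients, drop-out about 25%, 188 and 86 completers, limit 0.121 L, power 90% (Section 12.1); visits at months 1, 3, 6, 9 and 12 (Section 7).

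**Completers.** 250 × 0.75 = 187.5 and 115 × 0.75 = 86.25, which reproduces 188 and 86.

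**SD.** The protocol gives none, so the precision statement can only be back-solved. With f = √(1/188 + 1/86) = 0.1302 and a two-sided 95% interval:

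SD = 0.121 / [(1.960 + 1.282) × 0.1302] = 0.287 L.

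(Reading the limit as one-sided 95% gives 0.318 L. The coverage figures below do not depend on this choice; only the half-widths in litres scale with it.) The correct month-12 half-width is then 1.96 × 0.287 × 0.1302 = 0.0732 L.

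**Effect of compound symmetry.** Assume complete data and a separate mean for each group at each visit, which a month-12 group difference requires. The month-12 estimate is then the same under both structures, but the compound-symmetry standard error uses the average visit variance:

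k = SE(compound symmetry) / SE(correct) = √(mean of the five visit variances) / SD at month 12,

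and the coverage of a nominal 95% interval is 2Φ(1.96k) − 1.

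**Assumed SD path.** SD is linear in time from month 1 to month 12, with r = month-1 SD / month-12 SD. Worked case, r = 0.7: relative SDs 0.700, 0.755, 0.836, 0.918, 1.000; mean square 0.720; k = 0.849; half-width 0.849 × 0.0732 = 0.0621 L; coverage 2Φ(1.664) − 1 = 90.4%.

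**Simulation check.** 250 and 115 patients, 25% random monotone drop-out, assumed correlation 0.6 between visits, both structures fitted, 1,500 runs per row. The Monte Carlo standard error near 95% is √(0.95 × 0.05 / 1500) = 0.6 percentage points.

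| r | k | Half-width, L | Coverage, closed form | Simulated, compound symmetry | Simulated, unstructured |
|---|---|---|---|---|---|
| 1.2 | 1.108 | 0.0811 | 97.0% | 96.4% | 93.6% |
| 1.0 | 1.000 | 0.0732 | 95.0% | 95.4% | 94.9% |
| 0.9 | 0.948 | 0.0694 | 93.7% | 93.2% | 95.1% |
| 0.8 | 0.897 | 0.0657 | 92.1% | 91.0% | 95.0% |
| 0.7 | 0.849 | 0.0621 | 90.4% | 90.1% | 95.5% |
| 0.6 | 0.802 | 0.0587 | 88.4% | 87.7% | 94.6% |
| 0.5 | 0.758 | 0.0555 | 86.3% | 84.1% | 94.1% |

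The half-width and closed-form columns refer to compound symmetry with 188 and 86 completers. At r = 0.7 the simulated mean compound-symmetry standard error was 0.0293 against an actual spread of the estimate of 0.0350. The simulation follows the closed form, with somewhat lower coverage at the smallest ratios.

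**How likely is the trigger?** Five visits need 5 × 6 / 2 = 15 covariance parameters, to be estimated from about 250 + 115 = 365 patients. Non-convergence is unlikely there. It is somewhat more plausible in the separate spirometry run that excludes assessments failing the ATS quality criteria (Section 12.5), where data are thinner.

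**The case against.** The case against giving this weight is substantial, and most of it stands.

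- **Reach.** The rule sits in the exploratory efficacy section, and the model there has no treatment term. The spirometry model must differ at least by a group term, and no sentence gives it a covariance fallback. That it inherits the rule is a reasonable reading of Section 12.5, not a stated fact.
- **Direction.** The protocol does not say that variability rises with follow-up. With constant SD the rule does no harm, and with falling SD it is conservative.
- **Likelihood.** The rule is probably never used in the full data. A reader might point to the patients rolled over from the earlier studies, or to the 10- to 60-minute UPDRS scores, as likelier triggers. Neither bears on the FEV1 group difference: rollover patients are assigned only to CVT-301 (Section 9.2.1), and the UPDRS time curves are to be evaluated descriptively (Section 6).
- **Consequence.** A reader might infer that too narrow an interval would let a pulmonary effect be wrongly ruled out. The documents do not support that. The objectives are to characterise and to estimate, and 0.121 L appears only in the sample-size statement. No margin or test is declared.
- **Existing cover.** Section 12.6 offers ANCOVA at each visit as an example of a sensitivity analysis. It would use the month-12 variance alone and could expose the problem. The ATS-restricted spirometry result would also stand beside the all-data result. Section 12 lets the SAP override the protocol.

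What remains is that the protocol does state a fallback, and it is a poor one. Per-visit ANCOVA is a sensitivity example and does not replace it.

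**Conclusion.** The point holds in conditional form and is minor. If the unstructured model fails, the stated replacement misstates the month-12 interval whenever month-12 variance differs from the visit average. Over the assumed ratios from 0.9 to 0.5 the standard error is about 5% to 24% too small, and the half-width is 0.004 to 0.018 L too short (0.0732 minus 0.0694 to 0.0555). At a ratio of 1.2 the interval is about 11% too wide.

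These sizes rest on a back-solved month-12 SD of 0.287 L, a linear SD path, and separate group means at each visit. None of the three is stated in the protocol. Extending the point to spirometry rests on the word used in Section 12.5 to link the two models. The documents support a misstated interval in an unlikely contingency. They do not support a wrong safety decision.

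**What to change.** Replace the fallback sentence in Section 12.6, or override it in the SAP, with an ordered rule: unstructured; then heterogeneous Toeplitz; then heterogeneous AR(1); then heterogeneous compound symmetry; taking the first that converges. Use empirical (sandwich) standard errors whenever the structure is not unstructured. Add to Section 12.5 that the same rule applies to the spirometry MMRM, including the run that excludes assessments failing the ATS criteria.

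The heterogeneous structures do the main work, because they let month 12 keep its own variance. The order should be fixed before the data are analysed, since the study is open-label and a structure chosen after a failure would be post hoc.

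The cost is a sentence or two and a few lines of code and, if the fallback is used, possibly a slightly wider interval. No change to design, visits or sample size is needed.

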	
(TEAEs) will be summarized by body system and preferred term. For patients in the observational cohort, the AEs collected between TV/OV1 and TV/OV6 (or Early Withdrawal Visit) will be considered as TEAEs. Furthermore, the time of onset of the TEAEs will be summarized. For vital signs, ECG parameters, spirometry measurements, and DLco, the changes from pre-dose to post-dose assessments of the corresponding day will be calculated and described using descriptive statistics. For spirometry, DLco, and safety laboratory variables, the differences in pre-dose values between the study days will be described. Furthermore, the changes in the spirometry values and difference between the groups will be estimated using a Mixed Model for Repeated Measurements (MMRM) similar to the one used for the exploratory endpoint variables. The proportion of patients with abnormal spirometry values will be tabulated using different criteria for the threshold (e.g., at least 10% or 20% change from baseline at any single visit, at least 10% or 20% change from baseline on at least 2 consecutive visits). The proportions of patients meeting ATS quality criteria (and also for those 'rejected') will be summarized. All spirometry analyses will be performed both for all patients regardless of the ATS quality criteria and separately excluding the assessments not meeting the ATS quality criteria. Changes from baseline to follow-up in the rating scales for assessing suicidality, somnolence, and impulse control disorders will be summarized descriptively. Demographics and baseline characteristics will be summarized descriptively.
 
Exploratory Endpoint Analyses
 
The objectives related to the exploratory endpoints will primarily be assessed for the CVT-301-treated patients. The same objectives will be explored for the pool of CVT-301 naïve patients and patients who were previously enrolled in the CVT-301-002 or CVT-301-003 studies, if feasible.
 
The changes from baseline in continuous exploratory endpoint variables will be estimated using an MMRM. The model will include visit and the stratification variables (Hoehn and Yahr stage and screening FEV1 and/or FEV1/FVC) as fixed factors. The baseline value will be used as a covariate.
 
The categorical data will be primarily evaluated descriptively. Each visit will be evaluated separately for the categorical endpoints.
 
The exploratory endpoint data collected from the patients in the observational cohort will be summarized with descriptive statistics.

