CVT-301-treated patients will be followed in the clinic for the following efficacy measures: serial assessments of UPDRS Part 3 motor score following treatment in the clinic, the occurrence and severity of dyskinesia following treatment in the clinic, the occurrence of ON states during the post-treatment period, the 39-Item Parkinson's Disease Questionnaire (PDQ-39), the Patient Global Impression of Change (PGI-C) rating scale, the Schwab and England (S&E) Activities of Daily Living (ADL) score; UPDRS Part 2 score, and UPDRS Part 4 (Questions 32-35 and 36-39) score. In addition, the total daily ON time without dyskinesia, total daily ON time with troublesome dyskinesia, total daily ON time with non-troublesome dyskinesia, and total daily OFF time will be evaluated in the CVT-301-treated patients based on the PD Diary, which will be completed for the 3 consecutive days prior to SV2, TV/OV1, TV/OV2, TV/OV3, TV/OV4, TV/OV5, and TV/OV6.

All patients, regardless of treatment assignment, will undergo the safety assessments. Patient safety will be evaluated using adverse event (AE) reports, physical examination, vital signs (blood pressure [BP], heart rate [HR], and respiratory rate [RR]), clinical laboratory tests, 12-lead electrocardiograms (ECGs), spirometry, carbon monoxide diffusing capacity (DLco) maneuver, the Parkinson's Disease Impulsive-Compulsive Disorders Questionnaire (QUIP), the Epworth Sleepiness Scale, and the Columbia-Suicide Severity Rating Scale (C-SSRS).

The use of a randomized observational cohort in this study is to permit long-term contemporaneous temporal comparison to CVT-301-treated patients to describe any potential effects of CVT-301 with respect to lung function measurements. These control patients, who are eligible to use any approved treatments to manage their PD motor symptoms, represent a randomized study population that remains naïve to inhalation treatment (to avoid potential confounding interpretation of lung function data) for their PD which is required to ascertain the underlying variability in spirometry and DLco endpoints. Only a limited number of efficacy assessments will be evaluated in the patients randomized to the observational cohort. Selected efficacy measures to assess effects of CVT-301 will be evaluated in the open-label CVT-301-treated patients who use CVT-301 inhalation as a treatment of OFF symptoms.

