10.3.6.2. Observational Visit 4 for the Observational Cohort

Patients will report to the clinic after having taken their usual PD medications prior to the visit. The timing of administration of the usual morning dose of PD medication may be adjusted by the investigator to accommodate the patient's and/or clinic's schedule. Following their usual morning PD medication, no further PD medications will be used until following completion of

all assessments. The timing of arrival should be scheduled to increase the likelihood that patients will be in an ON state upon arrival (i.e., they should arrive to the clinic as shortly as feasible after taking their standard oral PD medications at home). Patients will bring to the clinic all usual PD medications.

The following procedures will be done:

- Confirm that the DLco assessment was performed within 2 weeks prior to OV4. If the DLco assessment has not been completed prior to the visit, the study visit must be re-scheduled.
- Record any changes in the usual PD medication dose/regimen.
- Record any changes in concomitant medications.
- Perform the PDQ-39, UPDRS Part 2, and S&E ADL (each preferably in the ON state and must be done prior to other study evaluations).
- Perform the C-SSRS, Epworth Sleepiness Scale, and the QUIP.
- Perform a brief physical examination.
- Record standard vital signs (BP, HR, and RR) and orthostatic vital signs (BP and HR).
- Perform a 12-lead ECG.
- Perform spirometry assessment (preferably in the ON state; however, if the patient is not in an ON state, perform the evaluation and record the motor state with each assessment).
- Collect blood for clinical laboratory tests including serum pregnancy test, if applicable. Document fasting status.
- Monitor patients for AEs.

The next visit will be scheduled and the clinic staff will arrange to call the patient 2 weeks prior to OV5 to monitor for AEs, to confirm the DLco assessment has been done/scheduled, and to confirm the next study visit. The DLco assessment will be scheduled to occur within 2 weeks prior to the next visit and should be performed while the patient is in an ON state (as reported by the patient to the pulmonary technician) at the pulmonary function facility. As part of the procedure, a slow vital capacity will be performed, followed by DLco, and then spirometry.

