10.3.8.2. Observational Visit 6 / Early Withdrawal Visit for the Observational Cohort

Patients will report to the clinic after having taken their usual PD medications prior to the visit. The timing of administration of the usual morning dose of PD medication may be adjusted by the investigator to accommodate the patient's and/or clinic's schedule. Following their usual morning PD medication, no further PD medications will be used until following completion of all assessments. The timing of arrival should be scheduled to increase the likelihood that patients will be in an ON state upon arrival (i.e., they should arrive to the clinic as shortly as feasible after taking their standard oral PD medications at home). Patients will bring to the clinic all usual PD medications.

The following procedures will be done:

- Confirm that the DLco assessment was performed within 2 weeks prior to OV6. If the DLco assessment has not been completed prior to the visit, the study visit must be re-scheduled.
- Record any changes in the usual PD medication dose/regimen.
- Record any changes in concomitant medications.
- Perform the PDQ-39, UPDRS Part 2, and S&E ADL (each preferably in the ON state and must be before other study evaluations).
- Perform a brief physical examination.
- Record standard vital signs (BP, HR, and RR) and orthostatic vital signs (BP and HR).
- Perform 12-lead ECG.
- Perform spirometry assessment (preferably in the ON state; however, if the patient is not in an ON state, perform the evaluation and record the motor state with each assessment).
- The C-SSRS, Epworth Sleepiness Scale, and QUIP should be completed.
- Collect blood for clinical laboratory tests including serum pregnancy test, if applicable. Document fasting status.
- Monitor patients for AEs.

Once all of the assessments are complete, schedule the patient for a DLco assessment 4 to 5 weeks after OV6. The DLco assessment should be performed while the patient is in an ON state (as reported by the patient to the pulmonary technician) at the pulmonary function facility. As part of the procedure, a slow vital capacity will be performed, followed by DLco, and then spirometry.

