11.2. Exploratory Efficacy Assessments

Exploratory efficacy will be evaluated primarily for the CVT-301-treated patients. Exploratory efficacy will be evaluated from both in-clinic, at-home assessments, and patient-reported assessments as outlined by the criteria below. A limited number of patient-reported assessments identified in the subsections below (i.e., the PDQ-39, UPDRS Part 2, and S&E ADL) will also be performed in the observational cohort.

In-Clinic Criteria:

- UPDRS Part 3 motor score
- Occurrence of an ON state during the 60-minute post-dose period and if an ON state occurs during the 60-minute post-dose, whether or not the patient is still in the ON state at 60 minutes post-dose

At-Home Criteria and/or Patient-Reported Assessments:

- Total daily OFF time at home, total daily ON time without dyskinesia, total daily ON time with non-troublesome dyskinesia, and total daily ON time with troublesome dyskinesia, based on the PD Diary.
- PDQ-39
- PGI-C
- S&E ADL
- UPDRS Part 2

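### PDQ-39, UPDRS Part 2 and S&E ADL are collected in both randomised arms, but the protocol plans no adjusted between-arm estimate for them: a cheap improvement, not an error

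*Protocol*

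**What the plan says.** Protocol Section 12.6 estimates change from baseline in continuous exploratory variables with an MMRM. Its fixed factors are given as: "The model will include visit and the stratification variables (Hoehn and Yahr stage and screening FEV1 and/or FEV1/FVC) as fixed factors". The baseline value is the covariate. Neither group nor group-by-visit is listed. The section then deals with the control arm: "The exploratory efficacy data collected from the patients in the observational cohort will be summarized with descriptive statistics". The synopsis lists the same model terms and has a matching sentence: "The exploratory endpoint data collected from the patients in the observational cohort will be summarized with descriptive statistics". It also says that the exploratory objectives are assessed mainly in CVT-301-treated patients.

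Section 11.2 names PDQ-39, UPDRS Part 2 and S&E ADL as the assessments shared with the observational cohort. Section 10.3.6.2 (month 6, observational cohort) instructs: "Perform the PDQ-39, UPDRS Part 2, and S&E ADL (each preferably in the ON state and must be done prior to other study evaluations". Section 10.3.8.2 (month 12) has an almost identical instruction.

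Section 5.2 shows that the limited role of the control arm here is intended: "Only a limited number of efficacy assessments will be evaluated in the patients randomized to the observational cohort". It gives the purpose of that cohort as comparison of lung function. The exploratory objectives in Section 6 for these three scales are changes from the baseline visit, with no comparison between arms.

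**The concern.** A mean change over 12 months in the CVT-301 arm mixes any effect of assignment to CVT-301 with the ordinary course of Parkinson's disease and with whatever else changes over a year of follow-up. A randomised concurrent group measured on the same scales at the same visits lets the shared part be subtracted. The protocol collects those data and then plans to describe them only.

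What is at stake is modest. Quality of life and daily function are exploratory in this trial. If the two arms are only summarised, readers will probably set the summaries side by side anyway, without baseline adjustment and without a confidence interval. A contrast added after the results are known would carry less weight in an open-label study than one fixed beforehand.

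**Working it through.** **1. Are the scales in both arms at matching times?** Yes, in the visit text and in the appendix tables.

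| Time | CVT-301 arm | Observational cohort |
|---|---|---|
| Baseline | Section 10.3.2.1 | Section 10.3.2.2 |
| 6 months | Section 10.3.6.1 | Section 10.3.6.2 |
| 12 months | Section 10.3.8.1 | Section 10.3.8.2 |

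All three scales appear in each cell.

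**2. Is a between-arm model specified for them?** No. Section 12.6 and the synopsis list visit, the stratification variables and baseline only. By contrast, Section 12.5 has the difference between groups in spirometry estimated with an MMRM described as similar to the efficacy one. The method is therefore already in the plan, but not applied to these scales.

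**3. The plan's own completer numbers (Section 12.1).** With 25% drop-out, 250 × 0.75 = 187.5 and 115 × 0.75 = 86.25. These agree with the stated 188 and 86.

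**4. Precision of an added contrast.** The document gives no SD for any of the three scales, so results are in units of the SD of the adjusted change. Under a normal approximation, SE = √(1/n₁ + 1/n₂) and the 95% CI half-width = 1.96 × SE.

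Rollovers from CVT-301-002 and CVT-301-003 go only to the CVT-301 arm (Section 9.2.1), so a randomised comparison has to leave them out. Their number is not given. I assume R = 20 enrolled, suggested by 250 − 2 × 115 (both approximate figures and no evidence of a true count), and R = 50 as a larger value. Naive completers are 0.75 × (250 − R): 0.75 × 230 = 172.5, taken as 172, and 0.75 × 200 = 150.

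| Case | n₁ / n₂ | SE | Half-width (SD) |
|---|---|---|---|
| Protocol's completers, R = 0 | 188 / 86 | √(1/188 + 1/86) = 0.130 | 0.26 |
| R = 20 (assumption) | 172 / 86 | √(1/172 + 1/86) = 0.132 | 0.26 |
| R = 50 (assumption) | 150 / 86 | √(1/150 + 1/86) = 0.135 | 0.27 |
| All enrolled observed, R = 0 | 250 / 115 | √(1/250 + 1/115) = 0.113 | 0.22 |

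The last row is a limit under full follow-up with no rollovers. The 6-month estimate should lie between the completer rows and that limit, because fewer patients will have left by then and an MMRM also uses data from patients who leave later.

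**The case against.** The strongest reply is that nothing here is wrong. No objective asks for a between-arm comparison on these scales, a one-arm model needs no group term, and Section 12.6 agrees with the synopsis. Section 12 already provides summaries by treatment group where applicable, so control data would be visible, and it says that additional analyses will be described in the SAP. That stands, and it is why the point is an improvement and not a fault. What remains is that the protocol fixes the model terms and the descriptive handling itself; it does not leave them open.

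A reader might infer from Section 5.2, "Selected efficacy measures to assess effects of CVT-301 will be evaluated in the open-label CVT-301-treated patients", that the protocol promises a controlled effect and then fails to estimate it. The text does not support this. The sentence does not name the three scales, it concerns treated patients, and the cohort's stated purpose is lung function.

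A reader might also infer that the contrast would isolate the effect of the drug. It would not. Background treatment may change after randomisation in both arms, but Section 9.4.2 restricts oral as-needed levodopa and the total daily levodopa of the modified regimen during the study only in the CVT-301 arm. Allocation is open (Section 9.2.1), and the scales are self-reported (Section 11.2.3) or scored by a rater who knows the allocation (Sections 11.2.5 and 11.2.6). The confidence interval would cover sampling error and none of this. Declining a modelled contrast for that reason is defensible, although open-label expectation affects the planned within-arm estimate as well.

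**Conclusion.** The point holds as an optional improvement. This protocol specifies no adjusted between-arm estimate with a confidence interval for three scales measured in both randomised arms at baseline, 6 and 12 months. The planned within-arm analysis remains valid and answers the stated objectives. The gain from a contrast is the removal of change shared by both arms, nothing more.

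The half-width would be about 0.26 SD with the protocol's twelve-month completers and changes little over the assumed range of rollovers. It should not be read as the best attainable, since fuller follow-up would bring it towards 0.22 SD. Whether this is precise enough to be informative cannot be judged from the document, which gives no SDs for these scales.

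The conclusion is limited to the protocol. The SAP, which takes precedence where the two differ, is not shown and may already contain such an analysis. The pulmonary objectives and their analysis are not affected.

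**What to change.** In Section 12.6 and the synopsis, keep the within-arm MMRM and the descriptive summaries. Add, for each of PDQ-39, UPDRS Part 2 and S&E ADL, one exploratory MMRM in the randomised CVT-301-naive patients of both arms, excluding rollovers from CVT-301-002 and CVT-301-003. Include group, visit, group-by-visit, baseline and the stratification factors. Report the CVT-301 minus observational difference with its 95% CI at 6 and 12 months.

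Label the result as exploratory, open-label and a comparison of assigned management strategies. State beside it that levodopa restrictions differ between the arms and that assessment is unblinded.

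The cost is a wording change in two places and one extra model per scale. No visit, assessment or treatment rule changes. The downside is that a confidence interval may look more conclusive than open-label data allow, which is why the label matters.
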